The *primary objective* of our study is to determine the effectiveness of serial infusions of intravenous (IV) ketamine in adults *with treatment resistant depression (TRD) - diagnosed with either Major Depressive Disorder or Bipolar Disorder* - at a slower infusion time than reported in previous studies. We expect that this approach alongside with the presence of a psychiatrist with Advanced Cardiac Life Support (ACLS) training will eliminate the need for continuing anesthetic monitoring during infusion, thus leading to a more cost-effective intervention. As part of this objective, we plan to recruit 30 individuals with Treatment Resistant Depression and conduct an open label, naturalistic study using slow infusions of ketamine over a time period of 40 minutes. **The duration of this study will be 12 weeks and will include twice weekly infusions over a period of 4 weeks and weekly infusions for the following 4 weeks of the study treatment period (8 weeks). There will also be a 4 week observational period post- treatment.**

Our *hypotheses* are that patients suffering from TRD receiving weekly slow IV infusions of ketamine (0.5 mg/kg) over 40 minutes will:

1. Report similar efficacy and better tolerability than those reported with conventional schemes of 3 infusions per week over a 12 day period.
2. Report less psychiatric side effects measured by changes in test scores on the Montgomery-Åsberg Depression Rating Scale (MADRS), Quick Inventory of Depressive Symptomatology (QIDS) and Young Mania Rating Scale (YMRS) compared to those previously reported with conventional schemes of serial ketamine infusions.
3. Report an almost immediate effect based on the PANSS and Q-LES-Q scales which will be administered after the 40 min infusion period.
4. Report less suicidal ideation measured by changes in scores on the Scale for Suicide Ideations (SSI; Beck et al., 1979), and the Suicide Status Form (SSF; Conrad et al., 2009) scores compared to that previously reported with conventional schemes of serial ketamine infusions.
5. Report a better global outcome of treatment measured by a decrease in scores on in the Clinical Global Impression Scale (CGI; Guy, 1976) score compared to that previously reported with conventional schemes of serial ketamine infusions.
6. Experience less hemodynamic changes in blood pressure and heart rate compared to than those previously reported with conventional schemes of serial ketamine infusions.

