7. Experience no cognitive impairment on the Brief Assessment of Cognition in Affective Disorders (BAC-A) following ketamine infusions. To our knowledge this hypothesis has not been previously assessed after an 8-week serial ketamine infusion treatment period.

Clinical relevance

Treatment Resistant Depression (TRD) is a major public health problem that constitutes a great burden for patients and mental health providers because of its prevalence, impact on people's quality of life and overall cost to the society (Nemeroff et al., 2007). Given the dearth of the research in the field of Ketamine treatment, more naturalistic follow-up studies focusing on ketamine's innovative antidepressant properties are warranted. Further, the findings of this study will provide health professionals with additional knowledge on the antidepressant properties of repeated ketamine IV infusions in both resistant Major Depressive Disorder (MDD) and Bipolar Disorder (BD). The current study will also help characterize responders from non- responders to ketamine, and will enable the assessment of the response and remission rates following ketamine intervention.

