Thus, in the current study we want to naturalistically explore the antidepressant effects of serial slow IV infusions (40 minutes) of ketamine at a dose of 0.5 mg/kg, over a treatment period of 8 weeks in an academic psychiatric hospital. This is a minimal sedation treatment. This dosage is the highest used so far in the literature and was selected because of its reported benefits in a psychiatric population. The dosage will be calculated using the patient's weight in kilograms. For dosing purposes, 0.5-0.9 round up to the next dose and from .01-0.49, we will round down to the lower dose. The primary outcome measure of this study will be *remission* estimated based on the severity of depressive scores (MADRS). After the 8 weeks of treatment, there will be a four week observational period. During the observational period, participants will receive treatment as usual and will be contacted over the phone for follow-up questions regarding their overall health status, mood and clinical state using MADRS, YMRS and CGI. They will also complete a neurocognitive task at the end of the 4 week observational period.

B. Innovation

The approach taken in the current study is novel for two reasons: 1) we are testing a novel dosage and time of infusion for the administration of slow infusion, repeated IV ketamine targeting TRD; 2) this is the first naturalistic study of repeated ketamine IV infusion for MDD and BD in a psychiatric setting. Furthermore, this will constitute the largest study conducted to date testing the antidepressant effects of repeated ketamine infusions in a combined population of MDD and BD patients with TRD.

C. Approach

The current project will exploit the feasibility of recruitment associated with ongoing studies at the University of Texas, Center of Excellence on Mood Disorder, Department of Psychiatry and Behavioral Science in Houston aimed at identifying the neural correlates of BD. The clinical sample will include individuals from various ethnic/racial backgrounds, reflecting the local community in the greater Houston area. We will use slow infusions of ketamine over a time

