period of 40 minutes. **We will conduct an open label, naturalistic study focusing on the antidepressant effects of ketamine twice a week for the first 4 weeks and then weekly injections up to week 8 in an academic psychiatric hospital (UTHealth Harris County Psychiatric Center - HCPC).** Thirty patients with clinically documented TRD will be screened for diagnosis with the depression and bipolar disorder subset of the Structured Clinical Interview for DSM-IV (SCID) (First et al., 1996) at baseline to establish the presence of a major depressive episode.

The administration of ketamine and urine tests will be carried out at the UTHealth Harris County Psychiatric Center (HCPC) in Houston, Texas. Routine blood tests and clinical/cognitive assessment will be done at the UTHealth Harris County Psychiatric Center (HCPC). Study drug will be provided in identical syringes, containing clear solutions including 1 mL of ketamine, e.g. 100 mg/mL with 9 mL of normal saline. A syringe will be used to provide IV applications of solution (). An ACLS psychiatrist will monitor the patient at HCPC. The administration of ketamine will be initiated by the anesthesiologist. The anesthesiologist will be present during the ketamine administration (40 minutes) and post-procedure (until patient is awake and anesthesiologist deems patient is clinically stable. The infusions will be conducted in our hospital during the mornings in a room set specially for this study. During the infusion, patients will be asked constantly about -how they feel and will receive constant attendance from a psychiatric nurse and the attending ACLS- trained psychiatrist. ECG and pulse oximetry monitoring will be maintained throughout the infusions to check for hemodynamic changes.

After completion of each 40 minute infusion, patients will rest for 2 hours under observation of the clinical nurse before being discharged to a responsible adult who will accompany the patient home. Based on Zarate et al.'s (2012)'s protocol infusions will be administered twice a week, every 3 days for the first 4 weeks of the treatment period.

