- 12) Pregnancy or Breast feeding. All female in reproductive age will undergo pregnancy tests. Female participants will be required to provide evidence of use of contraceptives during the course of the study.
- 13) Unable to understand the design and requirements of the study
- 14) Unable to sign the informed consent for any reason
- 15) An assigned responsible adult has provided assent to assist in patient's study participation. The responsible adult agrees to be present at each study appointment as well as provide transportation to study appointments for the patient.

Non responders

If a patient does not respond to the study treatment by their 4th treatment they will be removed from the study due to non-response. A successful response to study treatment will be at least a 30% reduction in MADRS scores from screening until the 4th treatment. Again if a patient does not respond by the 4th treatment, they will be excluded from the study.

Unanticipated Hospitalizations

If a patient needs to be hospitalized for worsening of symptoms or for their own personal safety, they will be removed from their study participation and their study treatment will end at that time.

Feasibility

Subject recruitment: Our center has access to a large patient pool (drawing from a metropolitan area of about 5.5 million people) and well-established ability to recruit patients with mood disorders. [name] is the department chair for Psychiatry and Behavioral Sciences and Director of the University of Texas, Center of Excellence on Mood Disorders. He successfully completed a large number of studies over the past 20 years with excellent recruitment of MDD and BD subjects at this site. We will also recruit participants through doctor referrals. Participants will be exclusively outpatients.

Funding of the study: given the preliminary nature of this study we plan to use departmental funding for the current study and then possibly apply for a larger grant later on once we have collected preliminary data and calculated optimal power/effect sizes for ketamine treatment in individuals with TRD.

Data analysis

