Normality assumptions for continuous variables will be examined. Where appropriate, outliers will be winsorised and log, square root or reciprocal transformations applied to achieve normality if appropriate. If normality cannot not been achieved, either untransformed or dichotomized scores were used. Baseline characteristics will be compared between responders and non-responders with the Mann-Whitney U test for continuous variables and the chi-square test for categorical variables. Changes between two time-points for continuous variables were tested with paired t tests, and associations between continuous variables will be quantified with the Spearman correlation coefficient. Random effects models will be performed to quantify changes in clinical score and its component items over time and to compare temporal differences between eventual responders and non-responders. Splines will be used to determine differences in the pattern of response over time among all patients and to identify the time at which there was no additional improvement in depressive symptoms. Additionally, the relationship between response status between baseline and end of study calculating sensitivity, specificity, and positive and negative predictive values will be reported. Time to relapse for patients who met response criteria at end point will be estimated with the Kaplan-Meier method. Analyses will be performed with IBM SPSS Statistics (version 19; SPSS, Chicago, Illinois) and SAS (version 9.2; SAS, Cary, North Carolina).

Study timetable

Activities	Months											
	1	2	3	4	5	6	7	8	9	10	11	12
Obtain IRB approval at UTHealth and HCPC		x	x									
Set up the Ketamine Ambulatory Clinic at HCPC			x	x								
Start recruiting patients and collecting data					x	x	x	x				
Analyses of initial dataset								x	x	x		
Submit a poster to International meeting with final results									x	x	x	
Submit result to high-impact peer-reviewed journals											x	x

Importance of the knowledge to be gained

Our findings will enhance our understanding of the safety, tolerability and efficacy of ketamine infusion in adults with TRD. Further it will help us understand the feasibility of this treatment in a psychiatric setting. The findings of the present study will also constitute an important foundation for future grant proposals investigating the efficacy of this intervention as a measure of suicide prevention.

*Women and Minority Inclusion in Clinical Research**Inclusion of Women*

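### Baseline predictors of response are assigned only a two-group comparison in 30 patients, which gives up about 36% to 66% of the information in MADRS change; a continuous analysis should lead and the response groups should be defined

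*Combined protocol and SAP*

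**What the plan says.** The Clinical relevance section states the aim: "The current study will also help characterize responders from non- responders to ketamine". The Data analysis section assigns one analysis to baseline characteristics: "Baseline characteristics will be compared between responders and non-responders with the Mann-Whitney U test for continuous variables and the chi-square test for categorical variables". It names no exact test and no model of MADRS change on baseline variables.

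Two other analyses come close. The first is that "associations between continuous variables will be quantified with the Spearman correlation coefficient", with no variables named. The second is a set of random effects models of the clinical score, used partly "to compare temporal differences between eventual responders and non-responders", so these are also grouped by response.

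The only response threshold in the document is under Non responders, where it serves as a rule for removal from the study: "A successful response to study treatment will be at least a 30% reduction in MADRS scores from screening until the 4th treatment". The Data analysis section does not say that this threshold forms its groups. It also speaks of eventual responders and of response at end point, without a threshold.

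On size, the objectives say "we plan to recruit 30 individuals with Treatment Resistant Depression", while the Approach section says "Thirty patients with clinically documented TRD will be screened for diagnosis", so the number analysed could be lower than 30. The Study design section states that no power or effect size was calculated.

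**The concern.** MADRS change is measured on a continuous scale. Cutting it at one threshold treats a patient just short of the cut like one who did not improve at all, and a patient just past it like one in full remission. When few patients fall on one side, the comparison rests on a handful of people. In a 30-patient study meant to supply effect sizes for later work, that is information the trial has already paid for.

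The chi-square test adds a smaller problem. If most patients respond, the tables become sparse. The Clinical assessment section collects race, education, religion and socioeconomic status, where small categories are likely.

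At stake is a secondary but stated product of the study: which baseline features go with response, and how strongly.

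**Working it through.** The plan gives no power figure to reproduce. Inputs from the documents are N = 30 and the named tests. Assumptions are two-sided 5% (no significance level is stated), bivariate normal predictor and MADRS change, all 30 patients analysed, and 50% to 90% responding. The expected response rate is not given. The background reports 9 of 10 responders in one series, but those patients had already responded to ketamine once.

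**1. Information kept by the split.** For a normal outcome cut so that a proportion p responds, efficiency is φ(z_p)² / [p(1 − p)], and effective N is 30 times that. At p = 0.5, for example, 0.3989² / 0.25 = 0.637.

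| Response rate | Efficiency | Loss | Effective N |
|---|---|---|---|
| 50% | 0.637 | 36% | 19.1 |
| 60% | 0.622 | 38% | 18.7 |
| 70% | 0.576 | 42% | 17.3 |
| 80% | 0.490 | 51% | 14.7 |
| 90% | 0.342 | 66% | 10.3 |

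**2. Power by simulation, N = 30, true correlation 0.5.** Spearman on the continuous change has about 77% power. Mann-Whitney on the split has:

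| Response rate | Power with the split | Power points lost |
|---|---|---|
| 50% | 57% | 20 |
| 70% | 52% | 25 |
| 80% | 43% | 34 |
| 90% | 27% | 50 |

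At a correlation of 0.3, Spearman has about 34%, against 22%, 21% and 18% at 50%, 70% and 80% response.

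**3. What 30 patients can detect at 80% power.** For a correlation, by Fisher's z: tanh[(1.96 + 0.84)/√27] = 0.49, or about 0.50 for Spearman. For the split, the standardised difference is (1.96 + 0.84)·√(1/n₁ + 1/n₂)/√0.955. This gives 1.05 (15 v 15), 1.14 (21 v 9), 1.31 (24 v 6) and 1.74 (27 v 3). Both approaches find only large associations.

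**4. Expected counts.** With k non-responders and a characteristic whose rarer level has share q ≤ 0.5, the smallest expected count is k·q when non-responders are the smaller group, so at most k/2. With k = 9 the ceiling is 4.5, so no 2x2 table reaches 5 with fewer than 10 non-responders. With 15 or 12 non-responders, a balanced factor gives 7.5 or 6.0, which is adequate.

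**5. One patient deciding a test.** For 0/24 v 1/6, Pearson chi-square is 30·(0·5 − 1·24)² / (24·6·1·29) = 17280/4176 = 4.14, p = 0.042. Fisher gives 6/30 = 0.20. For 0/27 v 1/3 the values are 0.002 and 0.10. With one patient among 7 non-responders the chi-square p is 0.065, and among 9 it is 0.12, so this needs 6 or fewer non-responders.

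**6. Type I error of the uncorrected chi-square, by enumeration.** At 24 v 6 it is 9.0% and 7.0% for characteristics of 5% and 10% prevalence. At 23 v 7 it is 1.6% and 2.7%. At prevalences of 20% to 50%, over eight splits, it lies between 3.1% and 5.8%.

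**The case against.** The case for leaving the plan alone is reasonable. None of the seven numbered hypotheses concerns predictors, the primary outcome is remission, and the study calls itself preliminary. The listed Spearman analysis could already cover continuous predictors against MADRS change. The small N limits any approach, and the linear normal model used above is the setting most favourable to a continuous analysis. All of that stands and keeps the point secondary. It does not remove it, because the plan never assigns Spearman to this aim and the loss is avoidable almost for free.

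Three stronger readings are tempting, and the documents do not support them:

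- A reader might infer that the groups are split at a 30% reduction. That threshold is written as a removal rule; the Data analysis section leaves its own definition and time point open. The information loss above depends on the response rate, not on the particular cut.
- A reader might infer that the chi-square tests are unsound throughout. Sparseness depends on the response rate and category balance. Inflated error appears only with about 4 to 6 non-responders and characteristics of roughly 5% to 10% prevalence.
- A reader might infer that the aim is lost. It is weakened: the split still has 57% power at a correlation of 0.5 if half the patients respond.

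**Conclusion.** The point holds as a secondary improvement. The only analysis assigned to baseline characteristics reduces MADRS change to two groups whose definition is not stated. That costs about 36% of the information at 50% response and 66% at 90%, or roughly 20 to 50 power points at a true correlation of 0.5. These figures rest on the assumed response rates, a two-sided 5% level, bivariate normality and 30 analysed patients; fewer patients would lower power under both approaches. Even after the change, only correlations near 0.5 or larger are likely to be detected.

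For categorical characteristics the conclusion is conditional. With fewer than 10 non-responders every 2x2 table falls below an expected count of 5, and with 6 or fewer a single patient can produce p < 0.05. Type I error is not generally inflated.

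**What to change.** In the Data analysis section:

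- **Main predictor analysis.** Relate baseline characteristics to continuous MADRS change at one early time point common to all treated patients. Use Spearman for continuous characteristics and Mann-Whitney or Kruskal-Wallis on the change for categorical ones, each reported with an interval.
- **Baseline MADRS.** Do not correlate it with its own change; model follow-up MADRS on baseline.
- **Responder table.** Keep it as description, state the response definition and time point it uses, and use an exact or mid-P test where expected counts fall below 5.

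One inconsistency has to be settled first. The Approach text and the Study design timetable list MADRS at baseline, weeks 4, 8 and 12 and the follow-up calls, with none at the 4th treatment. At two infusions a week that treatment falls at about week 2. The Non responders rule needs a score there, and patients removed under it may have no later one. These sections must be reconciled so that the early score is recorded.

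The cost is a few sentences, plus one scheduled rating that the removal rule already implies. There are two small downsides: early change answers a somewhat different question from end-point response, and a correlation is less familiar to clinicians than a two-group table.

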Routine blood tests will be performed in fasted state before the first ketamine infusion, prior to infusions at week 4 and at week 8. These tests aim to test the participants' overall health state. Blood samples will also be used for genetic testing and to measure levels of inflammatory markers. Samples will be stored at [REDACTED]. As stated in the consent form, participants will not receive any medical results or genetic counseling by providing a sample. All participants will undergo urine drug tests before each ketamine infusion.

Clinical questionnaires (e.g. MADRS) will be administered at baseline, at weeks 4, 8, and Week 12. The PANSS and Q-LES-Q scale will be administered after each ketamine infusion is completed. During the course of infusions, patients will receive treatment-as-usual from their primary psychiatrists as would be the case in a traditional therapeutic setting. There will be no changes in medication regimen throughout the 8 week treatment period as well as the 4 week observational follow-up period. Participants will be provided with a contact card directing them to the nearest ER/physician in case of emergency. Participants will be contacted weekly during the 4 week observational period to review the patient's health status and administer clinical scales. Upon conclusion of the intervention patients will be offered the opportunity to come back for maintenance sessions. The frequency of these sessions will depend on the patient's wishes and the physician's clinical judgment. The maximum session frequency will be once every month for a maximum of 12 months.

Assessment

The protocol consists of two components: clinical and cognitive assessments.

Clinical assessment

This evaluation will obtain family history and demographic data. Copies of any recent medical evaluations (past medical history, physical exam, etc.) will be requested from treating clinicians and health care providers. We will perform a urine drug screening (UDS) to rule out recent undisclosed use illicit substances. Demographic information is obtained through a standardized form and covers: age, race, gender, education (information both on siblings and their parents), religion, and socioeconomic status. Participants will fill out mood questionnaires rating the severity of the clinical symptoms.

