The BAC-A is based on the Brief Assessment of Cognition in Schizophrenia (BAC-S). The BAC-S has been validated both linguistically and psychometrically in a number of psychiatric populations, including patients with schizophrenia and BD (Cuesta et al., 2011; Hill et al., 2013; Kuswanto, Sum, & Sim, 2013; Salgado et al., 2007; Segarra et al., 2011). It has been shown to be as valid and sensitive as a traditional neuropsychological assessment and takes approximately 35 minutes to administer (Keefe et al., 2004; Velligan et al., 2004). Six of the 8 subtests of the BAC-A match those found in the BAC-S. These tests are the Token Motor Task, Symbol Coding, List Learning, Digit Sequencing Task, Category Instances (Animals) and

Controlled Oral Word Association Test (F and S-words), Tower of London (Keefe et al., 2004). In addition to these 6 subtests the BAC-A comprises the Emotion Inhibition Test (a modified version of the Emotional Stroop task (LaMonica, Keefe, Harvey, Gold, & Goldberg, 2010; Williams, Mathews, & MacLeod, 1996)) and the affective auditory verbal learning test (Affective interference test). The latter task is similar to the Affective Auditory Verbal Learning Test (AAVLT) (Snyder & Harrison, 1997). Assessments will be conducted prior to the treatment period, 4, and 8 weeks into the treatment. To avoid potential learning bias we will use parallel versions of the word lists for the Emotion Inhibition Test, Tower of London, and the Verbal Memory Tests to assess cognitive changes over the course of the ketamine treatment.

Study design

We will follow an AB design and clinical/cognitive assessments will be taken at baseline, week 4, week 8, and week 12. Given the preliminary nature of this treatment study this open label trial aims to generate an effect size for a subsequent RCT and/or future grant application. No *a priori* estimates of the power/effect size were therefore calculated.

Timeline	After Each Infusion	Baseline	Week 4	Week 8	Weekly Follow-up Phone Calls	Week 12
SCID-I		X				
Clinical scales (MADRS, CGI, YMRS)		X	X	X	X	X
PANAS, Q-LES-Q, self-report	X					
BAC-A		X	X	X		X
Blood tests/Sample		X	X	X		X
Urine drug test	X	X				

Study sample

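### Baseline MADRS appears to be both a tested predictor and the reference score that defines response, so its p value is not sound evidence that severity predicts response

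*Combined protocol and SAP*

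**What the plan says.** All places are in the combined protocol and SAP.

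- **Data analysis:** "Baseline characteristics will be compared between responders and non-responders with the Mann-Whitney U test for continuous variables". Baseline MADRS is neither named nor excluded. Associations between continuous variables are to be quantified with Spearman correlations. A random-effects model is also planned "to compare temporal differences between eventual responders and non-responders", with no separate criterion for that label.
- **Non responders:** "A successful response to study treatment will be at least a 30% reduction in MADRS scores from screening until the 4th treatment". No other response threshold is given.
- **Approach:** "Clinical questionnaires (e.g. MADRS) will be administered at baseline, at weeks 4, 8, and Week 12". The Study design table likewise shows MADRS at baseline and has no screening column.
- **Clinical relevance:** "The current study will also help characterize responders from non- responders to ketamine". The responder comparison serves this aim.
- **Objective and Study design:** "we plan to recruit 30 individuals with Treatment Resistant Depression and conduct an open label, naturalistic study", and "No *a priori* estimates of the power/effect size were therefore calculated". No significance level is stated.

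**The concern.** The Mann-Whitney test takes as its null that baseline MADRS has the same distribution in responders and non-responders. If response is computed from that same reading, the null can fail although severity has no bearing on percentage improvement. A rating that is too high by chance raises the patient's baseline score and also makes a 30% fall easier to reach. A rating that is too low does the reverse. Responders are therefore enriched for baselines that erred upwards.

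At stake is a reported finding that more severely depressed patients respond better to ketamine, when it may be regression to the mean. Characterising responders is a stated aim, and the study is meant to inform a later trial or grant application. The bias is systematic, so a larger study analysed in the same way would not average it away.

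**Working it through.** **Plan's own figure.** There is none to reproduce: the plan states no power, effect size, alpha or MADRS variability.

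**Inputs from the plan.** 30 patients; response is a reduction of at least 30%; Mann-Whitney test on baseline values.

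**Assumed inputs.** Two-sided alpha 0.05; observed baseline MADRS mean 32, SD 6; mean true reduction 45%, with SD between patients of 15, 25 or 35 percentage points; baseline reliability r (the share of observed variance that is true) from 1.0 down to 0.5.

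**1. Mechanism.** With baseline B and follow-up F, response means (B − F)/B ≥ 0.30, that is F ≤ 0.70 × B. For a patient whose true score is 32:

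- no error: F must be at most 0.70 × 32 = 22.4
- rated 4 points high: at most 0.70 × 36 = 25.2
- rated 4 points low: at most 0.70 × 28 = 19.6

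Baseline error alone moves the bar by 25.2 − 19.6 = 5.6 points.

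**2. Simulation.** True score T has SD 6√r and rating error has SD 6√(1 − r), which is 1.9, 2.7, 3.3 and 4.2 points at r = 0.9, 0.8, 0.7 and 0.5. B = T + error. F = T × (1 − p) + error, with p independent of T. Scores are integers limited to 0–60. There were 20,000 trials per cell, so the Monte Carlo standard error at 9% is √(0.09 × 0.91/20,000) = 0.2 points. Each cell gives the rejection rate, then the spurious responder minus non-responder difference in baseline MADRS.

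| r | SD of reduction 15 | SD 25 | SD 35 |
|---|---|---|---|
| 0.9 | 6.3%, 1.3 points | 5.1%, 0.6 | 5.1%, 0.4 |
| 0.8 | 10.4%, 2.0 | 6.9%, 1.2 | 5.7%, 0.8 |
| 0.7 | 14.3%, 2.6 | 9.1%, 1.6 | 7.1%, 1.2 |

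At r = 1.0 and SD 25 the rate is 4.3%, so with no rating error there is no excess. At r = 0.5 the rate was about 12–22% in the settings run. At SD 25, 73%, 87% and 94% of the rejections at r = 0.9, 0.8 and 0.7 show responders as more severe.

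**3. Separate reading.** If the tested baseline is a different rating from the one that defines response, the rates at SD 25 are 4.6%, 4.7% and 4.7% at r = 0.9, 0.8 and 0.7, and the difference is 0.1–0.2 points. Shared rating error is thus the cause under this null.

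**4. Other nulls** (3,000 trials each, shared reading).

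- Drop in points unrelated to severity: 13.8%, 8.0%, 5.2% and 4.1% at r = 1.0, 0.9, 0.8 and 0.7. At r = 0.9, 95% of rejections show responders as *less* severe.
- Follow-up score unrelated to baseline: 41–46%. A separate reading still gives 15–45%, because percentage change then depends on baseline by construction.

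**5. Spearman version.** Suppose percentage improvement is independent of severity, with no rating error. The change C = −pT still correlates with T, because cov(T, C) = −mean(p) × var(T). With T of mean 32 and SD 4 (true severity, again assumed) and p of mean 0.45 and SD 0.25:

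- cov = −0.45 × 16 = −7.2
- var(C) = 0.45² × 16 + 0.25² × (32² + 16) = 3.24 + 65 = 68.24
- correlation = −7.2/(4 × 8.26) = −0.22

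With mean 0.30 and SD 0.20 it is −0.18. This correlation cannot stand as evidence that severity predicts percentage response.

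**The case against.** **The shared reading is inferred.** The response rule says screening; the schedule says baseline. If these are two ratings, the excess under the proportional null is gone. This stands as a limit on the point. Nor is the schedule a complete list: at two infusions a week the fourth falls in week 2, yet no MADRS is listed between baseline and week 4. The absence of a screening MADRS is therefore suggestive, not conclusive. The natural reading remains one pre-treatment score, and the plan has to settle it.

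**The size is modest at ordinary reliability.** This also stands. A reader might infer that the test misleads in a fifth to a third of trials. Rates of 20–31% do arise with true SD 4 and error SD 5 or 6, but those imply reliabilities of 16/(16 + 25) = 0.39 and 16/(16 + 36) = 0.31. Nothing in the documents supports so noisy a baseline; the protocol describes the scale's psychometric properties as established.

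**The direction is not fixed.** A reader might infer that severe patients will always look like better responders. That holds under the proportional model only. The instability strengthens the case against a p value but weakens any claim about which way a result would err.

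**The stakes are low.** The comparison is exploratory, in a 30-patient open-label pilot, and MADRS is not named as a predictor. A reader might infer that a false severity finding would decide who enters the later trial. The plan says only that this study will supply an effect size and preliminary data, so that consequence is possible but not stated.

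**Conclusion.** The concern holds in limited form. On the plan's wording baseline MADRS is tested between groups that appear to be defined from the same reading, and no safeguard is stated. Under the proportional null and the assumed inputs, the nominal 5% test rejects in about 5–6% of trials at reliability 0.9, 6–10% at 0.8, 7–14% at 0.7 and 12–22% at 0.5. These rates rest on assumed MADRS variability and reliability and on a single pre-treatment reading.

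The rate and direction both depend on how improvement relates to severity, which the study does not know in advance. A p value for baseline MADRS is therefore not sound evidence that severity predicts response. The primary outcome, remission, is untouched. This is a cheap correction to make before analysis, not a threat to the study's main result.

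**What to change.** In the Data analysis section:

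1. Report baseline MADRS, total and items, by response group descriptively, without a p value.
2. Do not present Spearman correlations of baseline MADRS with MADRS change as evidence of prediction.
3. State whether screening and baseline MADRS are one reading. If two exist and a test is wanted, test the one not used to define response. This removes the shared-error bias only; the dependence shown under the other nulls remains.

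Baseline CGI could serve as the severity measure only if a severity item comparable across MDD and BD patients is collected. The Clinical assessment section describes the CGI as measuring global change and names a bipolar version for BD patients, so this cannot be assumed. The intercept–slope covariance of a random-effects model on the raw score is not a substitute: as step 5 of the working shows, absolute change covaries with severity even when percentage improvement does not.

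The cost is two or three sentences and no new data. The downside is that there would be no formal test of MADRS severity as a predictor of response, unless a second reading exists.
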